APPENDIX 11. HOSPITAL ANXIETY AND DEPRESSION SCORE (HADS)

Protocol RVT-1201-2002

		Hospital Anxiety and Depression Scale (H	* accoccmont		
		Name:	Date:		
	DAY IN LIEBE	Clinicians are aware that emotions play an important these feelings he or she will be able to help you more. This questionnaire is designed to help your clinician tunderline the reply which comes closest to how you numbers printed at the edge of the questionnaire. Don't take too long over your replies, your immediat accurate than a long, thought-out response.	to know how you feel. Read each item below and have been feeling in the past week. Ignore the	FOLDHERE	
A	D		Av a supplementary	Α	D
3 2 1 0		I feel tense or 'wound up' Most of the time A lot of the time From time to time, occasionally Not at all	I feel as if I am slowed down Nearly all the time Very often Sometimes Not at all		3 2 1 0
	0 1 2 3	I still enjoy the things I used to enjoy Definitely as much Not quite so much Only a little Hardly at all	I get a sort of frightened feeling like 'butterflies' in the stomach Not at all Occasionally Quite often	0 1 2 3	
3 2 1 0		I get a sort of frightened feeling as if something awful is about to happen Very definitely and quite badly Yes, but not too badly A little, but it doesn't worry me Not at all	I have lost interest in my appearance Definitely I don't take as much care as I should I may not take quite as much care I take just as much care as ever	3	3 2 1 0
	0 1 2 3	I can laugh and see the funny side of things As much as I always could Not quite so much now Definitely not so much now Not at all	I feel restless as if I have to be on the move Very much indeed Quite a lot Not very much Not at all	3 2 1 0	
3 2 1 0		Worrying thoughts go through my mind A great deal of the time A lot of the time Not too often Very little	I look forward with enjoyment to things As much as I ever did Rather less than I used to Definitely less than I used to Hardly at all		0 1 2 3
	3 2 1 0	I feet cheerful Never Not often Sometimes Most of the time	I get sudden feelings of panic Very often indeed Quite often Not very often Not at all	3 2 1 0	
0 1 2 3		I can sit at ease and feel relaxed Definitely Usually Not often Not at all	I can enjoy a good book or radio or television programme Often Sometimes Not often Very seldom		0 1 2 3
		Now eneck that you have	answered all the questions	٨	D
		Record form items originally published in - copyright © Munkagaard Internation This edition first published in 1994 by raft-Yelson Ni 1º Elsor Vantage London, Great Wen Ba GE Assessment is part of GL ful This farm may not be repushed by any means wi firmin permissional	TOTAL In a Psychiatrica Scientification, 67, 381–70, al Publishers List, Copenhagen, 1993. Meching Company List, now GL. Assessment Limited, ad Brentford TWN 9AG United Kingdom scatters www.ul-assessment.co.uk them first obtaining permission from the publisher. left-assessment on uk lading translations.		

APPENDIX 12. CLINICIAN-RATED QUICK INVENTORY OF DEPRESSIVE SYMPTOMATOLOGY

NAME:	 TODAY'S DATE:	

Please circle one response to each item that best describes the patient for the last seven days.

- 1. Sleep Onset Insomnia:
 - 0 Never takes longer than 30 minutes to fall asleep.
 - 1 Takes at least 30 minutes to fall asleep, less than half the time.
 - 2 Takes at least 30 minutes to fall asleep, more than half the time.
 - 3 Takes more than 60 minutes to fall asleep, more than half the time.
- 2. Mid-Nocturnal Insomnia:
 - 0 Does not wake up at night.
 - 1 Restless, light sleep with few awakenings.
 - Wakes up at least once a night, but goes back to sleep easily.
 - Awakens more than once a night and stays awake for 20 minutes or more, more than half the time.
- 3. Early Morning Insomnia:
 - 0 Less than half the time, awakens no more than 30 minutes before necessary.
 - 1 More than half the time, awakens more than 30 minutes before need be.
 - 2 Awakens at least one hour before need be, more than half the time.
 - 3 Awakens at least two hours before need be, more than half the time.
- 4. Hypersomnia:
 - O Sleeps no longer than 7-8 hours/night, without naps.
 - 1 Sleeps no longer than 10 hours in a 24 hour period (include naps).
 - 2 Sleeps no longer than 12 hours in a 24 hour period (include naps).
 - 3 Sleeps longer than 12 hours in a 24 hour period (include naps).

Enter the highest score on any 1 of the 4 sleep items (1–4 above) _____

- Mood (Sad):
 - 0 Does not feel sad.
 - 1 Feels sad less than half the time.

Protocol RVT-1201-2002

- 2 Feels sad more than half the time.
- 3 Feels intensely sad virtually all the time.
- 6. Appetite (Decreased):
- 0 No change from usual appetite.
- 1 Eats somewhat less often and/or lesser amounts than usual.
- 2 Eats much less than usual and only with personal effort.
- 3 Eats rarely within a 24-hour period, and only with extreme personal effort or with persuasion by others.
- 7. Appetite (Increased):
 - 0 No change from usual appetite.
 - 1 More frequently feels a need to eat than usual.
 - Regularly eats more often and/or greater amounts than usual.
 - 3 Feels driven to overeat at and between meals.
- 8. Weight (Decrease) Within The Last Two Weeks:
 - 0 Has experienced no weight change.
 - 1 Feels as if some slight weight loss occurred.
 - 2 Has lost 2 pounds or more.
 - 3 Has lost 5 pounds or more.
- 9. Weight (Increase) Within the Last Two Weeks:
 - 0 Has experienced no weight change.
 - Feels as if some slight weight gain has occurred.
 - 2 Has gained 2 pounds or more.
 - 3 Has gained 5 pounds or more.

Enter the highest score on any 1 of the 4 appetite/weight change items (6–9 above)

10. Concentration/Decision Making:

- 0 No change in usual capacity to concentrate and decide.
- 1 Occasionally feels indecisive or notes that attention often wanders.
- 2 Most of the time struggles to focus attention or make decisions.
- 3 Cannot concentrate well enough to read or cannot make even minor decisions.

11. Outlook (Self):

- O Sees self as equally worthwhile and deserving as others.
- 1 Is more self-blaming than usual.
- 2 Largely believes that he/she causes problems for others.
- 3 Ruminates over major and minor defects in self.

12. Suicidal Ideation:

- 0 Does not think of suicide or death.
- 1 Feels life is empty or is not worth

living.

- Thinks of suicide/death several times a week for several minutes.
- 3 Thinks of suicide/death several times a day in depth, or has made specific plans, or attempted suicide.

13. Involvement:

- 0 No change from usual level of interest in other people and activities.
- 1 Notices a reduction in former interests/activities.
- 2 Finds only one or two former interests remain.
- 3 Has virtually no interest in formerly pursued activities.

14. Energy/Fatiguability:

0 No change in usual level of energy.

Protocol RVT-1201-2002

Effective: 19JAN2022

- 1 Tires more easily than usual.
- 2 Makes significant personal effort to initiate or maintain usual daily activities.
- 3 Unable to carry out most of usual daily activities due to lack of energy.

15. Psychomotor Slowing:

- Normal speed of thinking, gesturing, and speaking.
- 1 Patient notes slowed thinking, and voice modulation is reduced.
- 2 Takes several seconds to respond to most questions; reports slowed thinking.
- 3 Is largely unresponsive to most questions without strong encouragement.

16. Psychomotor Agitation:

- No increased speed or disorganization in thinking or gesturing.
- 1 Fidgets, wrings hands and shifts positions often.
- 2 Describes impulse to move about and displays motor restlessness.
- 3 Unable to stay seated. Paces about with or without permission.

Protocol RVT-1201-2002 Effective: 19JAN2022

Enter the highest score on either of the 2 psychomotor items (15 or 16 above) _____

Scoring	Interpretation	
Enter the highest score on any 1 of the 4 sleep items (1 – 4)	 Normal	0 – 5
Item 5	 Mild	6 – 10
Enter the highest score on any 1 appetite / weight item $(6-9)$	 Moderate	11 – 15
Item 10	 Severe	16 – 20
Item 11	 Very Severe	21+
Item 12		
Item 13		
Item 14		
Enter the highest score on either of the 2 psychomotor items (15 and 16)		
Total Score (Range 0 – 27)	 LIT Cavithava atawa Madisal (

^{© 1986, 2000} UT Southwestern Medical Center, Dallas

APPENDIX 13. REVEAL LITE 2.0 (BENZA ET AL., 2020)

REVEAL Lite 2 is based on REVEAL 2.0, but includes only six noninvasive and modifiable parameters:

Protocol RVT-1201-2002 Effective: 19JAN2022

1. New York Heart Association (NYHA) or WHO functional class (FC);

```
FCI = -1, FCII = 0, FCIII = +1, FCIV = +2
```

2. Systolic BP;

```
SBP < 110 \text{ mm Hg} = +1, SBP \ge 110 = 0
```

3. Heartrate

```
HR > 96 \text{ bpm} = +1, \qquad HR \le 96 = 0
```

4. 6-min walk distance(6MWD);

```
≥ 440 min = -2,
320 - 440 min = -1
165 - 319 = 0
<165 min = +1
```

5. Brain natriuretic peptide (BNP)/N-terminal prohormone of brain natriuretic peptide (NT-proBNP);

```
BNP < 50 \text{ pg/mL} OR NT-proBNP < 300 \text{ pg/mL} = -2
BNP 50 - 199 \text{ pg/mL} = 0
BNP 200 - 799 \text{ pg/mL} = +1
BNP \geq 800 \text{ pg/mL} OR NT-proBNP \geq 1100 \text{ pg/mL}:+2
```

6. Renal insufficiency: if estimated glomerular filtration rate [eGFR] <60 mL/min/1.73 m2 or reported as "renal insufficiency," as assessed by the principal investigator when eGFR was unavailable +1); If ≥ 60 then score is 0

For the REVEAL Lite 2 assessment (with scores ranging from 1 to 14);

```
a score between 1 and 5 was considered low risk, a score of 6 or 7 was considered intermediate risk, a score of 8 or higher was considered high risk.
```

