9.3.1. Adverse Events of Special Interest

AESIs include:

- Severe constipation (and/or severe, persistent, or worsening abdominal pain)
- Depression/other significant mood-related disturbance (active suicidal ideation or behavior, severe depressive and/or anxious symptoms, other severe psychiatric TEAE)
- Elevations in hepatic enzymes (see Appendix 3)
- Diarrhea (see Appendix 2)

9.3.2. Time Period and Frequency for Collecting Adverse Event, Adverse Events of Special Interest, Serious Adverse Event Information

All SAEs will be collected from the signing of the ICF until the Follow-Up Visit at the time points specified in the SoA (Section 1.3). All AEs will be collected from the first dose of IP.

Medical occurrences that begin before the start of IP but after obtaining informed consent will be recorded on the Medical History/Current Medical Conditions section of the eCRF not the AE section.

All SAEs will be recorded and reported to the Sponsor or designee immediately and under no circumstance should this exceed 24 hours, as indicated in Appendix 14. The Investigator will submit any updated SAE data to the Sponsor within 24 hours of it being available.

Adverse events of special interest must be reported to the Sponsor should they meet the definition of an SAE, and all timelines for reporting of SAEs should be adhered to.

Investigators are not obligated to actively seek AEs or SAEs after conclusion of study participation. However, if the Investigator learns of any SAE, including a death, at any time after a patient has been discharged from the study, and he/she considers the event to be reasonably related to the IP or study participation, the Investigator must promptly notify the Sponsor.

9.3.3. Method of Detecting Adverse Events, Adverse Events of Special Interest, and Serious Adverse Events

The method of recording, evaluating, and assessing causality of AEs and SAEs and the procedures for completing and transmitting SAE reports are provided in Appendix 14.

Care will be taken not to introduce bias when detecting AEs and/or SAEs. Open-ended and non-leading verbal questioning of the patient is the preferred method to inquire about AE occurrences.

9.3.4. Follow-up of Adverse Events, Adverse Events of Special Interest, and Serious Adverse Events

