4.7.2. Definition of Baseline

The baseline value for 6MWD is the average of all walks prior to randomization.

Otherwise, for efficacy analyses the baseline value is defined as the last evaluation prior to randomization and for safety analyses, the baseline value is defined as the last evaluation prior to the first administration of study drug.

For ECG analyses, baseline is defined as the mean of triplicate assessments prior to the first administration of study drug. All available observations will be used in determining baseline, i.e. if there are less than 3 observations, the available observations will be used in determining the mean.

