7.4.5. Change from Baseline REVEAL Lite 2 Score

REVEAL Lite 2 includes 6 non-invasive variables: FC, vital signs (SBP and HR), 6MWD, NT-proBNP, and renal insufficiency (by eGFR). Individual component scores are defined as follows:

1. New York Heart Association (NYHA) or WHO functional class (FC):

FC Class	REVEAL2 FC Component Score
I	-1
II	0
III	+1
IV	+2

2. Systolic BP:

Systolic BP (mmHg)	BP Component Score
< 110	+1
≥ 110	0

3. Heart Rate

Heart Rate (bpm)	Heart Rate Component Score
> 96	+1
≤ 96	0

4. 6-min walk distance (6MWD);

6MWD (meters)	6MWD Component Score
> 440	-2
320 - 440	-1
165 – <320	0
<165	+1

5. N-terminal prohormone of brain natriuretic peptide (NT-proBNP);

NT-proBNP	REVEAL2 FC Component Score
<35.4 pmol/L <300 pg/mL	-2
≥35.4 and <129.8 pmol/L ≥300 and <1100 pg/mL	0
≥129.8 pmol/L ≥ 1100 pg/mL	+2

6. Renal insufficiency:

eGFR (mL/min/1.73 m ²)	Renal Component Score
< 60 or reported AE of Renal Insufficiency	+1
≥ 60	0

REVEAL Lite 2 Score= Sum of 6 component scores + 6 (with scores ranging from 1 to 14).

For subjects with missing component score(s) for #2 (SBP), #3 (HR), or #6 (eGFR), the REVEAL Lite 2 score will still be calculated as the sum of the 3 remaining component scores. Otherwise, if any other components are missing, the REVEAL Lite 2 score will be set as missing.

The REVEAL Lite 2 score will be analyzed using observed data and the same REML based MMRM model as specified in [Section 7.3.3](#).

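### SAP 7.4.5 lets a renal-insufficiency AE score +1 in REVEAL Lite 2 alongside an eGFR row that scores 0, drops Appendix 13's eGFR-unavailable condition, and states no precedence or time window

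*Protocol*

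**What the plan says.** **Protocol, Appendix 13.** The renal component is +1 if eGFR is below 60 mL/min/1.73 m². Reported renal insufficiency is a substitute, "as assessed by the principal investigator when eGFR was unavailable +1); If ≥ 60 then score is 0".

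**SAP 7.4.5.** The component table has two rows. The +1 row reads "< 60 or reported AE of Renal Insufficiency"; the 0 row is an eGFR of 60 or more, with no exception for AEs. The section introduces the score with "REVEAL Lite 2 includes 6 non-invasive variables: FC, vital signs (SBP and HR), 6MWD, NT-proBNP, and renal insufficiency (by eGFR", as protocol Section 9.1.10 also does. If SBP, HR or eGFR is missing, "the REVEAL Lite 2 score will still be calculated as the sum of the 3 remaining component scores". The total is the six components plus 6, analysed on observed data with the MMRM of SAP 7.3.3.

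**Timing.** SAP 4.7.2 states that "for efficacy analyses the baseline value is defined as the last evaluation prior to randomization". Under protocol Section 9.3.2, "All AEs will be collected from the first dose of IP", and "Medical occurrences that begin before the start of IP but after obtaining informed consent will be recorded on the Medical History/Current Medical Conditions section". Serious events are the exception: "All SAEs will be collected from the signing of the ICF until the Follow-Up Visit".

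**Declared changes.** SAP Section 11 does not mention the renal component.

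**The concern.** The SAP differs from Appendix 13 in two ways. It removes the condition that a report counts only without an eGFR, and it replaces the investigator's assessment with an AE record. Two programmers could score the same patient differently and both could defend the result.

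The AE source is also uneven in time. Baseline precedes randomization, and non-serious AEs start at first dose. Appendix 14 counts as an AE a condition first detected after dosing even if it was already present. A long-standing renal problem noted late could therefore score 0 before treatment and +1 afterwards with eGFR at or above 60 throughout. Nothing requires the AE to be ongoing, so an early event that resolved could still count at Week 24.

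At stake is the change from baseline in REVEAL Lite 2, which the SAP compares between arms.

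**Working it through.** **Inputs.** Component scores and the +6 constant: SAP 7.4.5. Renal rule: Appendix 13 and SAP 7.4.5. Arm size 30: SAP Section 3. The share of patients with a renal-insufficiency AE and eGFR of at least 60 at the visit is not in the documents; 0% to 10% per arm is assumed.

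**1. The plan's own figure.** In the order FC, SBP, HR, 6MWD, NT-proBNP, renal:

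- Minimum: (−1) + 0 + 0 + (−2) + (−2) + 0 + 6 = 1.
- Maximum: 2 + 1 + 1 + 1 + 2 + 1 + 6 = 14.

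The stated range of 1 to 14 is reproduced, with the renal component worth at most one point.

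**2. Renal change for a patient with a post-dose AE.** The AE is assumed to count from its onset onward. Example eGFR values are 50 (below the cut) and 75 (above it).

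| eGFR at baseline → Week 24 | Appendix 13 | SAP, 'or' row governs | SAP, '≥ 60' row governs |
|---|---|---|---|
| 75 → 75 | 0 − 0 = 0 | 1 − 0 = +1 | 0 − 0 = 0 |
| 50 → 75 | 0 − 1 = −1 | 1 − 1 = 0 | 0 − 1 = −1 |
| 75 → 50 | 1 − 0 = +1 | 1 − 0 = +1 | 1 − 0 = +1 |
| 50 → 50 | 1 − 1 = 0 | 1 − 1 = 0 | 1 − 1 = 0 |
| 75 → missing | 1 − 0 = +1 | 1 − 0 = +1 | 1 − 0 = +1 |

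The rules part only where follow-up eGFR is 60 or more. There the 'or' reading is one point higher than Appendix 13: it either creates a worsening or cancels an improvement. If the '≥ 60' row governs, the SAP agrees with Appendix 13 whenever eGFR is available.

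**3. Shift in an arm mean ('or' reading).** With k affected patients observed at the visit out of 30, the shift is k/30: 1/30 = 0.033, 2/30 = 0.067, 3/30 = 0.10 points.

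**4. Shift in the treatment difference.** This is approximately p(active) − p(placebo), where p is the affected share. All rates below are assumed.

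| p(active) | p(placebo) | Shift (points) |
|---|---|---|
| 5% | 5% | 0 |
| 5% | 2% | +0.03 |
| 2% | 5% | −0.03 |
| 10% | 3% | +0.07 |

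**The case against.** The strongest reply is that the SAP does not clearly award +1 with a normal eGFR. Its own table scores 60 or more as 0, and the section describes the component as based on eGFR. On that reading the AE words matter only when eGFR is missing, which is Appendix 13's rule, and the bias is nil. This stands as a possible reading. It does not remove the defect, because the SAP attaches no such condition to the AE words and does not say which row prevails.

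Other replies also hold:

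- Serious events are collected from consent, so the AE route is almost, not wholly, absent at baseline.
- Screening eGFR is an eligibility test (exclusion criterion 21), so a missing baseline eGFR should be rare.
- REVEAL Lite 2 is listed as an additional endpoint, outside the Hochberg procedure for the primary comparison.
- SAP Section 1 reserves Section 11 for substantial differences, so the omission there is a lesser matter.
- One point can move a patient from 5 (low risk) to 6 (intermediate), but SAP 7.4.5 plans only a numeric analysis. The split at 6 is used for baseline description and subgroups.

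A reader might infer that the rule is biased against the active arms, through diarrhea, volume loss and renal AEs. The documents do not support that. Protocol Section 4.7 reports dose-dependent nausea and diarrhea, but neither document gives a renal AE rate or names a renal event of special interest. That such AEs would follow, with eGFR still at or above 60, is conjecture.

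**Conclusion.** The point holds as an undeclared departure from Appendix 13 and as overlapping scoring rows without precedence or a time window. On the literal 'or' reading, and apart from the exception for pre-dose serious events, it can move within-arm change only towards worsening, by 0.033 points per affected patient in an arm of 30. One to three such patients, an assumed number, would give 0.03 to 0.10 points on a 1 to 14 scale. Bias in the treatment difference also needs unequal AE rates between arms and could go either way; at equal rates it is zero. The size is unknown and probably small. A firm statement that the SAP biases this endpoint would go too far, because the '≥ 60' row permits a reading with no bias. Severity: minor.

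**What to change.** In SAP 7.4.5:

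1. Score the renal component from the eGFR in the visit window whenever there is one: below 60 is +1, 60 or more is 0.
2. Only if eGFR is missing at that visit, use reported renal insufficiency, from the same sources at every visit including baseline: medical history not resolved by the visit, or an AE ongoing on the visit date. Taking history at baseline but only AEs later would create a new asymmetry. Appendix 14 does not count a stable pre-existing condition as an AE, so such a patient would appear to improve by a point.
3. Apply the missing-component rule only when neither eGFR nor a qualifying report is available, and correct its count: with eGFR alone missing, 6 − 1 = 5 components remain, not 3.
4. List in Section 11 any departure from Appendix 13 that is kept.

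The cost is a few sentences and a small programming change. No new data are needed: eGFR is already reported with the chemistry panel (SAP 8.3), and medical history and AE dates are already collected.

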APPENDIX 14. ADVERSE EVENTS: DEFINITIONS AND PROCEDURES FOR RECORDING, EVALUATION, FOLLOW UP, AND

Protocol RVT-1201-2002

Effective: 19JAN2022

Definition of Adverse Event

Adverse Event Definition

- An adverse event (AE) is any untoward medical occurrence in a patient, temporally associated with the use of investigational product (IP), whether or not considered related to the IP.
- NOTE: An AE can therefore be any unfavorable and unintended sign (including an abnormal laboratory finding), symptom, or disease (new or exacerbated) temporally associated with the use of IP.

Events Meeting the Adverse Event Definition

REPORTING

- Any abnormal laboratory test results (hematology, clinical chemistry, or urinalysis) or other safety assessments (e.g., electrocardiogram, radiological scans, vital signs measurements), including those that worsen from Baseline, considered clinically significant in the medical and scientific judgment of the investigator (i.e., not related to progression of underlying disease).
- Exacerbation of a chronic or intermittent pre-existing condition including either an increase in frequency and/or intensity of the condition.
- New conditions detected or diagnosed after IP administration even though it may have been present before the start of the study.
- Signs, symptoms, or the clinical sequelae of a suspected drug-drug interaction.
- Signs, symptoms, or the clinical sequelae of a suspected overdose of either IP or a concomitant medication. Overdose per se will not be reported as an AE/serious adverse event (SAE) unless it is an intentional overdose taken with possible suicidal/self-harming intent. Such overdoses should be reported regardless of sequelae.
- "Lack of efficacy" or "failure of expected pharmacological action" per se will not be reported as an AE or SAE. Such instances will be captured in the efficacy assessments. However, the signs, symptoms, and/or clinical sequelae resulting from lack of efficacy will be reported as AE or SAE if they fulfil the definition of an AE or SAE.

Events NOT Meeting the Adverse Event Definition

- Any clinically significant abnormal laboratory findings or other abnormal safety assessments which are associated with the underlying disease, unless judged by the Investigator to be more severe than expected for the patient's condition.
- The disease/disorder being studied or expected progression, signs, or symptoms of the disease/disorder being studied, unless more severe than expected for the patient's condition.
- Medical or surgical procedure (e.g., endoscopy, appendectomy): the condition that leads to the procedure is the AE.
- Situations in which an untoward medical occurrence did not occur (social and/or convenience admission to a hospital).
- Anticipated day-to-day fluctuations of pre-existing disease(s) or condition(s) present or detected at the start of the study that do not worsen.

Definition of Serious Adverse Event

If an event is not an AE per definition above, then it cannot be an SAE even if serious conditions are met (e.g., hospitalization for signs/symptoms of the disease under study, death due to progression of disease).

Protocol RVT-1201-2002

Effective: 19JAN2022

A serious adverse event is defined as any untoward medical occurrence that, at any dose:

1. Results in death

2. Is life-threatening

The term 'life-threatening' in the definition of 'serious' refers to an event in which the patient was at risk of death at the time of the event. It does not refer to an event, which hypothetically might have caused death, if it were more severe.

3. Requires inpatient hospitalization or prolongation of existing hospitalization

In general, hospitalization signifies that the patient has been detained (usually involving at least an overnight stay) at the hospital or emergency ward for observation and/or treatment that would not have been appropriate in the physician's office or outpatient setting. Complications that occur during hospitalization are AEs. If a complication prolongs hospitalization or fulfills any other serious criteria, the event is serious. When in doubt as to whether "hospitalization" occurred or was necessary, the AE should be considered serious.

Hospitalization for elective treatment of a pre-existing condition that did not worsen from Baseline is not considered an AE.

4. Results in persistent disability/incapacity

- The term disability means a substantial disruption of a person's ability to conduct normal life functions.
- This definition is not intended to include experiences of relatively minor medical significance such as uncomplicated headache, nausea, vomiting, diarrhea, influenza, and accidental trauma (e.g., sprained ankle) which may interfere with or prevent everyday life functions but do not constitute a substantial disruption.

5. Is a congenital anomaly/birth defect

6. Other situations:

- Medical or scientific judgment should be exercised in deciding whether SAE reporting is
 appropriate in other situations such as important medical events that may not be immediately life
 threatening or result in death or hospitalization but may jeopardize the patient or may require
 medical or surgical intervention to prevent one of the other outcomes listed in the above definition.
 These events should usually be considered serious.
- Examples of such events include invasive or malignant cancers, intensive treatment in an emergency room or at home for allergic bronchospasm, blood dyscrasias, or convulsions that do not result in hospitalization, or development of drug dependency or drug abuse.

Recording and Follow Up of Adverse Events and/or Serious Adverse Events

Adverse Event and Serious Adverse Event Recording

- When an AE/SAE occurs, it is the responsibility of the Investigator to review all documentation (e.g., hospital progress notes, laboratory reports, and diagnostics reports) related to the event.
- The Investigator will then record all relevant AE/SAE information in the case report form.
- It is not acceptable for the Investigator to send photocopies of the patient's medical records to Sponsor in lieu of completion of the AE/SAE case report form page.
- There may be instances when copies of medical records for certain cases are requested by Sponsor. In this case, all patient identifiers, with the exception of the patient number, will be redacted on the copies of the medical records before submission to Sponsor.
- The Investigator will attempt to establish a diagnosis of the event based on signs, symptoms, and/or other clinical information. Whenever possible, the diagnosis (not the individual signs/symptoms) will be documented as the AE/SAE.

Assessment of Intensity

The Investigator will make an assessment of intensity for each AE and SAE reported during the study and assign it to 1 of the following categories:

- Mild: An event that is easily tolerated by the patient, causing minimal discomfort, and not interfering with everyday activities.
- Moderate: An event that causes sufficient discomfort and interferes with normal everyday activities.
- Severe: An event that prevents normal everyday activities. An AE that is assessed as severe should not be confused with a SAE. Severe is a category utilized for rating the intensity of an event; and both AEs and SAEs can be assessed as severe.
- An event is defined as 'serious' when it meets at least 1 of the predefined outcomes as described in the definition of an SAE, NOT when it is rated as severe.

Assessment of Causality

- The Investigator is obligated to assess the relationship between IP and each occurrence of each AE/SAE.
- A "reasonable possibility" of a relationship conveys that there are facts, evidence, and/or arguments to suggest a causal relationship, rather than a relationship cannot be ruled out.
- The Investigator will use clinical judgment to determine the relationship.
- Alternative causes, such as underlying disease(s), concomitant therapy, and other risk factors, as well as the temporal relationship of the event to IP administration will be considered and investigated.
- The Investigator will also consult the Investigator's Brochure and/or Product Information, for marketed products, in his/her assessment.
- For each AE/SAE, the Investigator must document in the medical notes that he/she has reviewed the AE/SAE and has provided an assessment of causality.
- There may be situations in which an SAE has occurred and the Investigator has minimal information to include in the initial report to the Sponsor. However, it is very important that the Investigator always make an assessment of causality for every event before the initial transmission of the SAE data to the Sponsor.

Assessment of Causality

- The Investigator may change his/her opinion of causality in light of follow-up information and send a SAE follow-up report with the updated causality assessment.
- The causality assessment is one of the criteria used when determining regulatory reporting requirements.

Follow Up of Adverse Events and Serious Adverse Events

- The Investigator is obligated to perform or arrange for the conduct of supplemental measurements and/or evaluations as medically indicated or as requested by the Sponsor to elucidate the nature and/or causality of the AE or SAE as fully as possible. This may include additional laboratory tests or investigations, histopathological examinations, or consultation with other health care professionals.
- If a patient dies during participation in the study or during a recognized follow-up period, the Investigator will provide the Sponsor with a copy of any post-mortem findings including histopathology.
- New or updated information will be recorded in the originally completed case report form.
- The Investigator will submit any updated SAE data to the Sponsor within 24 hours of receipt of the information.

Reporting of Serious Adverse Events

Serious Adverse Event Reporting to the Sponsor via an Electronic Data Collection Tool

- The primary mechanism for reporting an SAE to the Sponsor will be the electronic data collection tool.
- If the electronic system is unavailable, then the site will use the paper SAE data collection tool (see next section) in order to report the event within 24 hours).
- The site will enter the SAE data into the electronic system as soon as it becomes available.
- After the study is completed at a given site, the electronic data collection tool will be taken off-line to prevent the entry of new data or changes to existing data.
- If a site receives a report of a new SAE from a study patient or receives updated data on a previously reported SAE after the electronic data collection tool has been taken off-line, then the site can report this information on a paper SAE form (see next section) or to the Sponsor's medical monitor/SAE coordinator by telephone.
- Contacts for SAE reporting can be found on the Contact Information page.

Serious Adverse Event Reporting to the Sponsor via Paper Case Report Form

- Email transmission of the SAE paper case report form is the preferred method to transmit this information to the Sponsor's Medical Monitor or the SAE Coordinator.
- In rare circumstances and in the absence of facsimile equipment, notification by telephone is acceptable with a copy of the SAE data collection tool sent by overnight mail or courier service.
- Initial notification via telephone does not replace the need for the Investigator to complete and sign the SAE case report form pages within the designated reporting time frames.
- Contacts for SAE reporting can be found on the Contact Information page.
